The number of spine surgeries performed in the United States has steadily increased in the past several decades.^{15,16} Between 1990 and 2000, there was a 220% increase in the number of spinal fusion surgeries¹⁶ and in 2002, there were more than 1 million spinal procedures performed in the United States.¹⁷⁻¹⁹ In 2004 alone, spinal fusion surgery alone generated costs exceeding \$16 billion in hospital charges.²⁰ Despite the staggering numbers of patients having spine surgery, the incidence of patients that will fail to achieve adequate pain relief after lumbar spinal surgery (failed back surgery syndrome (FBSS)) is commonly quoted in the range of 10%-40%.^{10,21-23} Treatment guidelines are scant for FBSS, in large part due to the complexity and heterogeneity of the entity, with a vast array of differing underlying etiologies.²⁴ A practical understanding of the etiology of FBSS can be categorized into preoperative, intraoperative, and postoperative factors. Intraoperative surgical factors include poor technique, wrong-level surgery, and inability to achieve the proposed aim of the surgery. Post-operative factors for FBSS include: progressive disease (e.g., new disc herniation or spondylolisthesis), epidural fibrosis, and surgical complications including nerve injury, hematoma, or infection. Although anatomic factors may play a role in failure to derive analgesic benefit after lumbar spine surgery, psychosocial risk factors have been found to be much more powerful in predicting low back pain disability than structural abnormalities.²⁵ Psychological factors that have been shown to correlate with poor analgesic outcomes (FBSS) after spine surgery include significant levels of anxiety and depression, poor coping, and somatization.²⁶⁻²⁹ Social factors that have been associated with FBSS include the presence of a personal injury claim or worker’s compensation claim.^{26,30-33} While some of these studies used a prospective design and adequate sample sizes, many of them were retrospective in nature - making temporal relationships difficult to infer, and there was great variety in the selection of patient-reported outcomes and questionnaires to draw their associations.

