Inclusion (ALL) 
 • Able to Read and Speak English • Between 22-70 years old • Stable dose (or not on) of adjunctive pain medications for at least 2 weeks prior to QST • Able to provide informed consent 	Exclusion (ALL) 
 • Diagnosis of a medical condition that isn't minor or stable • Current litigation regarding a medical illness • Drug or alcohol abuse • Severe physical impairment • Co-morbid medical conditions that may impair physical functional status • Psychiatric condition that may impair functional status (active psychosis or suicidal ideation) • Pregnant or nursing • Liver failure, cirrhosis, hepatitis • Severe cardiovascular disease
Inclusion (ALL) QST 
 • Right-Handed • Willingness to refrain from alcohol and nicotine on the day of QST • Willingness to refrain from pain meds 12 hours prior to QST 	Exclusion (ALL) QST 
 • Current or recent (6 months) use of artificial fingernails or nail enhancements • Neuropathy or loss of feeling in upper or lower extremities

 Willingness to refrain from strenuous exercise that would cause muscle or joint soreness 48 hours prior to QST 	
Inclusion (Healthy) In addition to (ALL) above: n/a	Exclusion (Healthy) In addition to (ALL) above: 
 Diagnosis of a chronic pain syndrome (mild is fine; but less than 3/10 pain score on any body region) Score >3 on FM 2011 survey
Inclusion (FBSS) In addition to (ALL) above: 
 Has chronic low back pain (+/- leg pain) for > 6 months after a lumbar spine surgery Low back pain severity greater than or equal to 4/10 	Exclusion (FBSS) In addition to (ALL) above: 
 Involved in litigation for low back pain or previous low back surgery
Inclusion (LSS) In addition to (ALL) above: 
 Low back pain severity greater than or equal to 4/10 Willingness to participate in longitudinal follow-up questionnaires post-op 	Exclusion (LSS) In addition to (ALL) above: 
 Involved in litigation for low back pain or previous low back surgery History of a previous back surgery LSS is due to spinal cancer-related diagnoses LSS is urgent or emergent

Eligibility (MRI): In addition to eligibility within each group

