Inclusion: 
 Able to lie still in an MRI scan for up to 2 hours Normal vision acuity or corrected vision No contradictions to MRI screening form 	Exclusion: 
 Severe Claustrophobia BMI > 40 or unable to lie comfortably in the MRI Implantable Device (Cardiac pacemaker/defibrillator), Gastric Pacemaker, Neurostimulation Device, Bladder Stimulator, Cochlear Implant) Heart Heart Valve Replacement Hearing Aid, Lyric Device Hydrocephalus/Spinal Shunt Aneurysm/Vascular Clips Stents, Filters, or Coils Seizure History Bullet, BB, or Foreign Body Eyelid Spring/Wire History of Metal in Eyes Medication/Insulin Pump Prosthetic Device Body Piercings (permanent) Medication Skin Patch
---	--

	
 • Dentures/Partials • Kidney Disease • Kidney/Liver Transplant • Liver Cirrhosis / Cancer • Permanent Eyeliner • Vascular IV Access 
 ○ FEMALE PATIENTS: • I.U.D. Device
--	---

Medical conditions that are not minor or stable examples: uncontrolled hypertension/diabetes

Severe physical impairment examples: Blindness, deafness, paraplegia

Co-morbid medical conditions example: autoimmune disorders, history of non-skin malignancy

Severe cardiovascular disease: history of a heart attack, severe coronary artery disease, unstable angina, congestive heart failure, severe valvular abnormalities

Psychiatric conditions: Stable anxiety and depression are NOT considered exclusions

2. **Withdrawal/Termination criteria:** If during the study, the patient develops or shows any of the exclusion criteria for their cohort, they will be withdrawn by the investigator. They may voluntarily withdraw at any time.
3. Patients may participate in another research study while enrolled in this study.

E. Specific methods and techniques used throughout the study

Study Procedures:

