Methods to reduce risks associated with QST (as conducted before and during MR/PET imaging) will include the following: a) the proposed settings and methods are widely used and have been shown to be safe in extensive use worldwide; b) participants are told that they are free to stop any testing procedure at any time; c) research personnel receive extensive training and follow detailed standardized operating procedures that ensure safety; d) the maximum pressures applied are set to be below levels that would cause tissue injury; e) the MAST and IPC-1000 automated pressure stimulators include redundant software, electrical, and mechanical safety features to ensure that the amount of pressure applied does not cause tissue damage, including a button that the patient or researcher can push to immediately release the device from his/her thumb; f) testing is automatically stopped if participants report maximal pain (e.g., 100 on 0 to 100 scale). During the performance of the MR, the volunteers will be monitored at all times by research personnel associated with the project (research assistant, radiology technologists) or the investigators themselves. Participants will be asked to complete and sign a safety screening form used by the KUMC Hoglund Brain Imaging Center and will be instructed to bring or wear clothing without metal fasteners, and remove jewelry and any other metal objects from their body. All people (including staff) who enter the exam room that contains the magnet are hand screened for magnetic material before entering. Participants will wear foam earplugs or headphones to reduce the loud noises made by the scanner. Participants will be able to communicate with the examiner throughout the scan. If needed, the participant can be removed immediately from the bore of the magnet. The MRI machine is operated within FDA guidelines so the potential for inducing peripheral nerve stimulation is low. Women of childbearing potential will be required to take a urine pregnancy prior to MRI testing. If refused, the participant will be excluded from any further aspects of the study. In addition, all the volunteers will have direct access to the phone numbers and pagers of the study coordinator and the responsible clinicians ([name]), as well as a 24-hour contact number (emergency room services). These phone numbers are provided in the consent forms. One copy of the signed consent form is provided to the subjects. They will be encouraged to contact the investigators if they notice any unusual symptoms or untoward side effects.

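### The withdrawal rule keeps the entry exclusion criteria in force after surgery, so it can remove surgical failures before the 6-month outcome is recorded

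*Combined protocol and SAP*

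**What the plan says.** Section II.D.2 (Withdrawal/Termination criteria) is mandatory: "If during the study, the patient develops or shows any of the exclusion criteria for their cohort, they will be withdrawn by the investigator". It sets no time limit and does not separate leaving a research procedure from leaving the study.

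The criteria it refers to are in section II.D.1. For the lumbar spine surgery (LSS) cohort they include "Involved in litigation for low back pain or previous low back surgery" and "History of a previous back surgery". The list for all participants adds substance abuse and "Psychiatric condition that may impair functional status (active psychosis or suicidal ideation".

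Section B (Background and Significance) ties one of these to the outcome under study, failed back surgery syndrome (FBSS): "Social factors that have been associated with FBSS include the presence of a personal injury claim".

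Section II.C defines success as a halving of pain from baseline to 6 months. The primary test compares failure proportions between FM-high and FM-low, 50 patients each, by a two-sided chi-squared test at 0.05. The power calculation uses all 100 patients. The plan has no allowance for attrition and no missing-data method. It does not say whether a withdrawn patient still gives a 6-month pain score, or whether that patient counts as a failure, as missing or as excluded.

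Separately, the paragraph on reducing QST and MRI risks says of a woman who declines the urine pregnancy test before MRI: "If refused, the participant will be excluded from any further aspects of the study".

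**The concern.** Exclusion criteria define who enters a cohort. Used again as withdrawal triggers during follow-up, they let events after the operation decide whose outcome is observed. Where such an event is more common among patients who did badly, the loss is informative: failures leave and successes stay.

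Two consequences follow. The failure proportions are understated. The FM-high versus FM-low contrast may also be distorted, and how far depends on whether removal differs by FM group. Differential removal is plausible. Section B describes affective symptoms as part of centralized pain, so a trigger such as suicidal ideation need not fall evenly on the two groups.

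The criterion on earlier back surgery raises a simpler problem. It has no time anchor, so after the index operation its words fit every LSS patient. That conflicts with the planned 6-month follow-up in sections II.B, II.E (Follow Up) and V.B.

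**Working it through.** **Inputs.** From section II.C: 50 patients per FM group, two-sided alpha 0.05, and failure rates (FM-low vs FM-high) of 0.10 vs 0.50, 0.15 vs 0.45 and 0.17 vs 0.43, with stated power 0.99, 92% and 82%. The share *f* of failures withdrawn before 6 months is an assumption, shown at 5%, 10% and 20%. No successes are withdrawn, and withdrawn patients drop out of the test.

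**Step 1: reproduce the plan's power.** With p̄ the pooled failure proportion,

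power = Φ{ (|p₂ − p₁| − 1.96·√[p̄(1−p̄)(1/n₁ + 1/n₂)]) / √[p₁(1−p₁)/n₁ + p₂(1−p₂)/n₂] }.

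For 0.17 vs 0.43: (0.26 − 1.96 × 0.0917)/0.0879 = 0.914, and Φ(0.914) = 0.820. The other two scenarios give 0.918 and 0.996. All three agree with the plan.

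**Step 2: remove failures.** In each affected group n′ = 50(1 − pf) and p′ = p(1 − f)/(1 − pf). For 0.17 vs 0.43 at f = 0.20:

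- FM-low: n′ = 50(1 − 0.034) = 48.3; p′ = 0.136/0.966 = 0.141.
- FM-high: n′ = 50(1 − 0.086) = 45.7; p′ = 0.344/0.914 = 0.376.
- The risk difference goes from 0.260 to 0.236, and power from 0.820 to 0.751.

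**Step 3: power over the range.**

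| Removal | f | 0.10 vs 0.50 | 0.15 vs 0.45 | 0.17 vs 0.43 |
|---|---|---|---|---|
| none | 0 | 0.996 | 0.918 | 0.820 |
| equal in both groups | 0.05 | 0.995 | 0.907 | 0.805 |
| equal in both groups | 0.10 | 0.993 | 0.895 | 0.789 |
| equal in both groups | 0.20 | 0.987 | 0.865 | 0.751 |
| FM-high only | 0.05 | 0.994 | 0.893 | 0.780 |
| FM-high only | 0.10 | 0.990 | 0.862 | 0.735 |
| FM-high only | 0.20 | 0.975 | 0.779 | 0.626 |

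**Step 4: effect on the estimates.**

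- *Overall failure rate, equal removal.* It is 30% in every scenario and falls to 28.9%, 27.8% and 25.5% at f = 0.05, 0.10 and 0.20.
- *Risk difference, equal removal.* At f = 0.20 it shrinks from 0.40, 0.30 and 0.26 to 0.363, 0.272 and 0.236.
- *Odds ratio, equal removal.* The odds of failure in each group are multiplied by (1 − f), so the ratio is unchanged at 9.0, 4.64 and 3.68.
- *Odds ratio, FM-high only.* It is multiplied by (1 − f). At f = 0.20 it becomes 7.2, 3.71 and 2.95. Removal only from FM-low would inflate it by 1/(1 − f).

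**Step 5: how many patients.** The scenarios imply 100 × 0.30 = 30 failures, so f = 0.20 in both groups is 6 patients. In FM-high only it is 50 × p₂ × 0.20 = 5.0, 4.5 or 4.3 patients.

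**The case against.** Several stronger readings are tempting, and the documents do not support them.

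- **A reader might infer that the rule withdraws every operated patient.** The natural sense of the earlier-surgery criterion is surgery before the index operation, and the LSS list refers to the index operation separately. Follow-up, payment and the end of study all run to 6 months after surgery. This is a wording defect, not a likely loss of the cohort.
- **A reader might infer that failures are in fact being removed.** No withdrawal frequency is given. Eligibility is self-reported, the study schedule places the eligibility form at baseline only, and follow-up is by phone or email questionnaire. The rule permits selective removal; the documents do not show that it happens.
- **A reader might add sensory loss and severe impairment as triggers.** Section B does list "surgical complications including nerve injury, hematoma, or infection" among post-operative causes of FBSS. But "Neuropathy or loss of feeling in upper or lower extremities" is a QST criterion, and LSS patients have QST once, before surgery. Severe impairment is illustrated by blindness, deafness and paraplegia, which are not ordinary correlates of missing 50% relief. Stable anxiety and depression are expressly not exclusions.
- **A reader might link pregnancy-test refusal to surgical failure.** Imaging of LSS patients is pre-operative, so it cannot be so linked.
- **A reader might conclude that the loss could never be assessed.** Pain is collected at 2 weeks, 1 month and 3 months, and the schedule lists stop-study and consent-withdrawal forms, so withdrawals could be counted and bounded.

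The objection also stands on size: under the main assumption power is barely touched, and equal removal leaves the odds ratio alone. What it does not answer is that the sentence is mandatory, that litigation in particular can follow a poor result, and that no rule protects the 6-month outcome of a withdrawn patient.

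**Conclusion.** The concern holds as a risk built into the rule, not as a demonstrated loss. It should be fixed but does not invalidate the study.

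The bias rests on three assumptions: that withdrawn patients give no 6-month score and leave the analysis, that failures are withdrawn more often than successes, and that the share lies somewhere near the 5% to 20% shown. If the plan instead counted withdrawn patients as failures, the understatement calculated above would not arise, but the plan does not say so.

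With equal removal the damage is to the failure proportions and, in the plan's scenarios, to the risk difference. The odds ratio is biased only if removal differs by FM group. The power loss is trivial for 0.10 vs 0.50. It is material for 0.17 vs 0.43, where power is below the plan's 80% mark at f = 0.10 with equal removal (0.789), and at f = 0.05 if only FM-high loses failures (0.780).

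The pregnancy-test sentence is a separate matter: avoidable loss of participants, not bias from surgical failure.

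**What to change.** Amend section II.D.2 to say:

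- The exclusion criteria are assessed at enrolment, and the earlier-surgery criterion means surgery before the index operation.
- A later event may end a specific research procedure, but the participant stays in questionnaire follow-up and in the 6-month analysis unless consent is withdrawn.

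Add to section II.C how patients without a 6-month score enter the primary test. Include a report of withdrawals by reason and FM group, and a sensitivity analysis that bounds the result by counting them first as failures and then as successes.

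Separately, reconcile the sentence on pregnancy-test refusal with the questionnaire-only parts of the study and with the pregnancy exclusion in section II.D.1.

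The cost is a one-paragraph protocol amendment and a short addition to the analysis section. It needs no extra visits or staff.

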There is a growing appreciation of the importance of augmented central nervous system (CNS) pain processing and centralized pain in many chronic pain states.^{34,35} **The term “centralized pain” has been used to describe any CNS dysfunction or pathology that may be contributing to the development or maintenance of chronic pain.**³⁵⁻³⁷ The pain experienced by individuals with centralized pain is typically multifocal (with a high current and lifetime history of pain in many bodily regions), rated as more severe, and characterized by neuropathic pain descriptors. Beyond pain, co-existing somatic symptoms including memory difficulties, fatigue, and sleep disturbances as well as cognitive/affective symptoms (e.g., catastrophizing, anxiety, depression) are frequently observed.^{36,38,39} Another hallmark of the centralized pain phenotype is the frequent presence of hyperalgesia and/or reduced or absent endogenous analgesia.⁴⁰⁻⁴² Data from quantitative sensory testing (QST) studies suggest a wide, bell-shaped distribution in pain sensitivity across the general population. Most, but not all, individuals with centralized pain fall on the right side of this curve and have QST findings consistent with notable hypersensitivity (hyperalgesia and allodynia).^{36,43-49} Some of the chronic pain conditions where QST evidence of widespread hypersensitivity is consistently seen include fibromyalgia (FM), irritable bowel syndrome, tension headache, low back pain, temporomandibular joint disorder, interstitial cystitis, and vulvodynia.⁵⁰⁻⁶⁰

[figure not shown]
The prominent role of central factors in chronic pain is substantiated by the fact that there is no chronic pain condition in which the extent of tissue damage or inflammation alone (e.g., as evaluated by an X-ray or MRI) accurately predicts the presence or severity of pain.⁶¹⁻⁶⁵ Many people have “normal” radiographs or MRIs yet report unbearable pain, while others have significant radiographic or MRI findings yet report no pain. It has been theorized that this discrepancy exists because individuals with chronic pain display variable degrees of CNS pain amplification and the current 2011 Fibromyalgia

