Overall Study Design. For Aims 1 and 2, a prospective, observational study will recruit 100 men and women with chronic low back pain (+/- leg pain) who are scheduled to undergo lumbar spine surgery at the University of Kansas Medical Center (KUMC). 50 will participate in phenotypic characterization and 50 will participate in phenotypic characterization and quantitative sensory testing (QST) procedures. After screening, informed consent, and enrollment into the study, all subjects will undergo an evaluation which includes a comprehensive battery of questionnaires for patient phenotyping that will assess symptoms including pain, physical function, depression, anxiety, and catastrophizing symptoms. QST parameters will only be performed on half of the cohort of lumbar spine surgery patients. Patient phenotyping and QST procedures will take place in one visit pre-operatively. At two weeks, one month, three months, & six months post-surgery, we will administer one questionnaire to determine analgesic response to surgery. This will establish longitudinally-designated post-surgical analgesic outcome groups (see Statistical Analysis section for definitions). Instead of just a three month time point that is often used in analgesic trials, a six month time point was chosen to give adequate time for recovery and response to surgery. Phenotyping and QST will also be done in a cross-sectional manner on 50 age and sex-matched healthy controls and 50 age and sex-matched patients with an established diagnosis of FBSS (established-FBSS) to compare to the longitudinally-designated post-surgical analgesic outcome groups. For Aim 3, 30 men and women with chronic low back pain (+/- leg pain) who are scheduled to have lumbar spine surgery at KUMC will undergo pre-operative functional, structural, and chemical neuroimaging studies. 15 age and sex-matched healthy controls and 15 age and sex-matched established-FBSS patients will also undergo the same neuroimaging studies to compare to the longitudinally-designated post-surgical analgesic outcome groups. Patients for Aim 3 will be recruited from both the prospective and cross-sectional cohorts enrolled for Aims 1 and 2. The goal of the studies in Aim 3 are to investigate whether pre-operative functional, structural, and chemical neuroimaging findings known to be associated with centralized pain and indicative of CNS amplification are associated with the centralized pain phenotype and possibly predictive of failure to achieve pain relief after lumbar spine surgery. We acknowledge that these studies are exploratory and may be underpowered but feel that they will at a minimum provide critical preliminary data for future studies.

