Quantitative Sensory Testing (QST): Pain testing for a variety of parameters will be performed using various pain testing devices as described below. QST requires significant training of personnel, manuals of operations and procedures, scripting, and other techniques to get good reproducible results. Participants will be familiarized with the procedures and equipment before testing. Half of the patients (n=50) patients undergoing lumbar spine surgery will complete this testing pre-operatively. Healthy controls and patients with established FBSS will only perform this testing once. Patients who participate in Aim 3 studies will also have a portion of the QST listed below as part of their MRI experimental protocol (see below).

- *Generalized Pressure Pain Sensitivity.* Pressure pain threshold (PPT) at the mid-trapezius (an unaffected site in all cohorts) will serve as the primary measure of generalized pain sensitivity in all participants (*trap-PPT*). Increased pain sensitivity at remote or unaffected body areas is strongly suggestive of central pain mechanisms and occurs in many chronic pain conditions. Here, PPT will be measured bilaterally using a digital algometer with a 1-cm² rubber probe (Somedic, Hörby, Sweden). Pressure will be manually increased at a rate of 30-50 kPa/s (1000 kPa max). Participants will press a response button to indicate their first sensation of pain. Pressure intensity at the time of button press is recorded as the PPT. Measurements will be conducted 3x/side (20-s intervals) with means used for analysis. Pressure-evoked pain at the thumbnail will serve as a secondary measure of generalized pain sensitivity, using the Multimodal Automated Sensory Testing (MAST) System, a computerized QST device developed at the University of Michigan, and currently being employed in several clinical trials, including the NIH MAPP network.

My mentors have extensive experience using thumbnail pressure as an evoked pain stimulus. The MAST system will deliver an ascending series of 5-s duration stimuli at 25-s intervals, beginning at 0.50 kg/cm² and increasing in 0.50 kg/cm² intervals up to tolerance or a maximum of 10 kg/cm². Pain intensity will be rated after each stimulus on a 0 (no pain) – 100 (extreme pain) numerical rating scale (NRS). Pressure pain threshold and tolerance will be determined from this procedure, as well as the PAIN50, the pressure intensity that provokes a response halfway between threshold and tolerance.

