- *Localized Pressure Pain Sensitivity.* Localized or regional pain sensitivity, measured as a PPT (see above for method), will be determined for the lumbar spine in all cohorts as an indicator of peripheral sensitization. The lumbar spine will be stimulated over the bilateral lumbar spine areas at approximately L4-5.
- *Cuff Algometry.* Large volume, deep muscle sensitivity^{165,166} will be assessed by pressure cuff using a MRI-compatible rapid cuff inflator (Hokanson, Bellevue, WA).¹⁶⁷⁻¹⁶⁹ Participants will

first receive an ascending series of cuff pressures, starting at 20 mmHg and increasing in 20 mmHg steps (10-s pressures, 20-s intervals) to tolerance or a maximum of 400 mmHg. Each pressure will be rated after deflation on a 0-100 NRS. These pain ratings will be used to interpolate a series of 8 tolerable cuff pressures that will be delivered in randomized order and rated individually. Stimulus response curves will be constructed for each participant and used for analysis, along with several derived variables: *cuff-PPT*, *cuff-Pain50*, and *cuff-TOL*. In addition, tonic pain induced by continuous cuff pressure will be assessed (*tonic-Cuff*). Each participant's individually calibrated Pain40 pressure (i.e., pressure that evokes a 40/100 pain rating) will be applied for 6-min to one gastrocnemius muscle. Pain intensity and unpleasantness ratings will be obtained every 60-s. The same P40 pressure will be applied for 6 minutes in the MRI scanner.

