Magnetic Resonance Imaging: In addition to QST, patients enrolled in Aim 3 studies will also undergo four different neuroimaging procedures (all in one visit) to identify brain regions and associated neurotransmitters operative in pain processing and modulation: 1) *Functional connectivity MRI* (fcMRI) will be performed at rest, 2) *Proton magnetic resonance spectroscopy* (¹H-MRS) of the insula (anterior and posterior) as well as the anterior cingulate cortex (ACC) assessing combined glutamate and glutamine (Glx), 3) *Evoked pain fMRI* will be used with evoked thumb nail pressure pain to avoid affected body sites as well as tonic cuff pressure (at Pain 40), and 4) *Voxel based morphometry to assess gray matter volume in the primary somatosensory cortex (S1) and motor (M1) cortex*. The specific neuroimaging methods have

been employed heavily by [name] research group and are described in detail in their published research.^{54,58,74,76,122,131-141} We will utilize these exact imaging protocols and adapt them for use in the Siemens Skyra 3T scanner at the KUMC Hoglund Brain Imaging Center. These different procedures investigate varying aspects of the brain's involvement in pain processing and modulation that will complement the QST methods by further providing a comprehensive picture of the neurobiological presence of pain centralization. Comprehensive training and familiarization procedures will be completed prior to MRI to reduce anxiety. Participants will be instructed that the neuroimaging can be stopped at any time if a procedure becomes unbearable. As for QST, all procedures have been evaluated for safety and are well tolerated by chronic pain patients and controls. Neuroimaging will require approximately 2 hours to complete.

All study procedures are solely for research purposes and none are part of usual standard therapy. No study procedures will be billable to insurance companies.

Timeline: **See last page.**

1. Risk/benefit assessment:

Physical risks:

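### Nothing in the plan makes the trapezius a pain-free site in surgical or FBSS patients, so a low trapezius threshold may partly reflect local pain

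*Combined protocol and SAP*

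**What the plan says.** Section II.E, Quantitative Sensory Testing, sets the primary measure: "Pressure pain threshold (PPT) at the mid-trapezius (an unaffected site in all cohorts) will serve as the primary measure of generalized pain sensitivity". The reason follows in the same paragraph: "Increased pain sensitivity at remote or unaffected body areas is strongly suggestive of central pain mechanisms". Thumbnail pressure is the secondary generalized measure. Lumbar threshold is measured separately and read as peripheral sensitization.

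Under Cuff Algometry, each person's Pain40 pressure "will be applied for 6-min to one gastrocnemius muscle". The side is not stated, and the site of the ascending cuff series is not named.

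The eligibility table (II.D.1) limits regional pain in one cohort only. Healthy controls must have "less than 3/10 pain score on any body region" and a 2011 FM Survey score of 3 or less. The established-FBSS criterion reads "Has chronic low back pain (+/- leg pain) for > 6 months after a lumbar spine surgery", and the Overall Study Design admits leg pain in the surgical cohort too. The nearest QST exclusion for patients is neuropathy or loss of feeling in the limbs, which is not the same as pain.

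Background and Significance says: "The pain experienced by individuals with centralized pain is typically multifocal". In the MRI section, evoked-pain fMRI "will be used with evoked thumb nail pressure pain to avoid affected body sites", with the tonic cuff used alongside. The Aim 2 analyses treat all QST results as continuous measures and reuse the Aim 1 comparisons, with no term or subset for pain at the test site.

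**The concern.** The central reading of a low trapezius threshold depends on the site being away from the pain. The plan accepts this distinction, since it reads the lumbar threshold as peripheral and picks the thumbnail for fMRI to stay clear of affected sites. For its primary measure it asserts the condition without securing it.

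Patients who also have neck, shoulder or upper-back pain can enter the surgical and FBSS cohorts, while controls are screened for regional pain. If trapezius pain is commoner in AOC-failures than in AOC-successes, local tenderness would add to any true difference between them and favour the hypothesis. Hypothesis 2b also expects failures to resemble established FBSS, and shared local tenderness could contribute to that resemblance. The calf cuff raises the same question in a patient whose tested leg is the painful one.

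**Working it through.** **Is the site condition secured?** Setting the sections side by side:

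- *Eligibility (II.D.1):* no limit on trapezius-area pain in surgical or FBSS patients; a limit in controls only.
- *QST methods (II.E):* no record of pain at the test site on the day of testing. The section mentions manuals and scripts, which are not among the documents.
- *Analysis (II.C, Aim 2):* no adjustment, restriction or sensitivity analysis for site pain.
- *Expected pain pattern (I.B):* multifocal in the target phenotype. In the pilot, FBSS patients had a mean FM score of 13.7 and 60% (21 of 35) were FM-positive, on a score that includes the Widespread Pain Index.

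The condition is not secured, and the protocol's own material makes pain beyond the low back likely. The documents do not say how often that pain is in the trapezius or calf.

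**How large could the effect be?** The plan states no figure to reproduce, so this is an illustration.

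Assumptions that are not in the documents:
- Local pain lowers the threshold by d = 0.4 to 0.8 SD.
- Trapezius-area pain is present in 60% of failures, 30% of successes and 10% of controls. The 60% is not taken from the FM-positive rate, which does not measure trapezius pain.
- There is no true central difference.

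Group sizes: 50 surgical patients have QST. Each of the three power scenarios in II.C averages 30% across equal halves, for example (0.10 + 0.50)/2 = 0.30, if these are read as failure proportions. That gives 15 failures and 35 successes. There are 50 controls.

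Formulas: spurious shift = (difference in prevalence) × d; SE = √(1/n₁ + 1/n₂) in SD units; two-sided rejection rate = Φ(shift/SE − 1.96) + Φ(−shift/SE − 1.96).

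*Failure versus success (15 v 35):* SE = √(1/15 + 1/35) = 0.309.
- d = 0.4: shift 0.30 × 0.4 = 0.12; ratio 0.389; 0.058 + 0.009 = 0.067.
- d = 0.8: shift 0.24; ratio 0.778; 0.119 + 0.003 = 0.122.

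*Success versus controls (35 v 50):* SE = √(1/35 + 1/50) = 0.220.
- d = 0.4: shift 0.20 × 0.4 = 0.08; ratio 0.363; 0.055 + 0.010 = 0.065.
- d = 0.8: shift 0.16; ratio 0.726; 0.109 + 0.004 = 0.112.

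Hypothesis 2b predicts similarity in this second comparison, so the bias works against it.

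*Failure versus established FBSS:* if 60% is also assumed for FBSS, the shift is zero.

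*Wider range for 15 v 35:* with a prevalence difference of 0.1 to 0.4 and d of 0.25 to 0.8 SD, the rejection rate runs from 5% (essentially no inflation) to 18%.

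**The case against.** The strongest reply is that trapezius tenderness in a patient with lumbar disease may be the very signal sought. The protocol treats multifocal pain as part of centralized pain, and the Widespread Pain Index is a component of the FM score, its main measure of interest. Restricting to participants without regional pain then conditions on part of the exposure and removes high-FM patients selectively. This stands. It limits the restricted comparison to a supportive role and rules out adjusting for the full FM score.

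The rationale also refers to sites that are remote or unaffected, and the trapezius is remote from the lumbar spine whatever its pain status. That stands, but the plan goes further and claims the site is unaffected in every cohort.

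Aim 2 does not rest on the trapezius alone. Thumbnail pressure, conditioned pain modulation (thumbnails) and temporal summation (forearm or hand) serve as cross-checks. The plan does not say how discordant results would be read.

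On the cuff, the calf is named only for the tonic stimulus, whose pressure is calibrated to the individual, which partly offsets local sensitivity. The cuff is described as a deep-muscle measure, and the neuropathy exclusion will remove some patients with leg symptoms. The cuff point is therefore secondary.

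A reader might infer a much larger error from comparing established FBSS with controls. At 50 v 50, with 60% against 10% prevalence, the shift is 0.20 to 0.40 SD, the SE is 0.20 and the rejection rate is 17-52%. The analysis section does not list that test. It compares failures with successes, failures with FBSS, and successes with controls. Only the general statement of purpose sets FBSS against controls.

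**Conclusion.** The claim about the trapezius is unsupported for surgical and FBSS patients, and the plan has no check for pain at the test site. A low threshold may therefore partly reflect local pain. The tonic cuff has a lesser version of the same gap.

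Under the stated assumptions, the false-positive rate is about 7-12% for failure versus success and about 6.5-11% for success versus controls, against a nominal 5%. Every prevalence and effect size behind these figures is assumed, and smaller values give almost no inflation.

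A reader might conclude that local pain will be read as central amplification, or that Aim 2's inference is lost. The documents support neither: they give no prevalence of trapezius or calf pain, and other measures are taken away from the back and leg. Nor do they require a different primary measure. The thumbnail is chosen to avoid affected sites in the fMRI section only, and in multifocal pain the hands may hurt too.

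**What to change.** 1. Delete or qualify the statement that the trapezius is unaffected in all cohorts.
2. Flag pain at each test site, either from the baseline Widespread Pain Index (assumed to cover these regions) or with one field on the QST record sheet. The Study Schedule already collects the 2011 FM Survey at baseline in every cohort.
3. Keep the trapezius threshold as primary. Pre-specify a sensitivity comparison in participants without local trapezius pain, and name the thumbnail threshold, already collected, as the check on the primary result.
4. Apply the tonic cuff to the leg without pain where there is one, record the side, and flag participants with pain in both legs.
5. Do not adjust for the full FM score, since it is the exposure of interest.

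The cost is a change of wording, a field or two on the QST sheet and one extra analysis, with no new procedure. The restricted subset will be smaller and will under-represent high-FM patients, because regional pain is part of the FM score. Its result should be reported as supportive only.
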